6.7.3.4. Other Analyses

The KM method will be used to estimate the OS curve for each treatment arm. Point estimates and CIs for the first quartile, median, and third quartile for the OS curve of each arm will be estimated. The OS rates at 1, 2, and 3 years for each arm will be estimated and compared using a normal approximation for the difference between the rates.

A stratified Cox proportional hazard model (stratified by nature of disease and prior (neo)adjuvant endocrine therapy) with treatment as a factor will be used to estimate the HR between the abemaciclib + NSAI group and the placebo + NSAI group, and the corresponding CI and Wald p-value.

A restricted mean difference analysis on OS will be conducted as described for PFS in Section [6.7.2.3.2.](#)

Follow-up time for OS will be defined from the date of randomization and will use the inverse of the censoring rules for OS. The median follow up time will be calculated using the KM method.

6.7.3.5. Exploratory Pooled Overall Survival Analyses

The ITT populations of JPBL and JPBM will be combined to form a pooled population. Overall survival analyses will be performed on this population. The purpose of these analyses is to

evaluate whether adding abemaciclib to the appropriate endocrine therapy improves survival for patients with locally advanced or metastatic disease.

6.7.4. Other Secondary Endpoints

6.7.4.1. Objective Response Rate, Disease Control Rate, and Clinical Benefit Rate

Objective response rate (ORR), disease control rate (DCR), and clinical benefit rate (CBR) are summary measures of best overall response (BOR) as defined by RECIST v1.1. BOR is derived from time point responses. All time point responses observed while on study treatment and during the short term follow up period (but before the initiation of post discontinuation therapy) will be included in the derivation. The one exception includes patients who receive surgery and/or radiotherapy for locally advanced breast cancer. For these patients, only those time point responses occurring prior to surgery/radiotherapy will be included in the derivation.

Each patient's BOR will be categorized as CR, PR, SD, progressive disease (PD), or not evaluable (NE). For patients with bone-only nonmeasurable disease (see Section 6.4.2), BOR will be limited to CR, SD, PD, and NE. Patients with SD will be further classified as SD \geq 6 months or SD <6 months. Stable disease \geq 6 months includes all patients with a best response of SD and a PFS time of \geq 6 months. A BOR of CR or PR will not require confirmation.

Objective response rate is the proportion of patients with a BOR of CR or PR. Clinical benefit rate is the proportion of patients with a BOR of CR or PR, or SD \geq 6 months. Disease control rate is the proportion of patients with a BOR of CR, PR, or SD. Patients with bone-only nonmeasurable disease cannot have a best response of PR, thus ORR will be reported for both the ITT population and the subset of patients with measurable disease.

For each of these rates, point estimates and confidence intervals (using the normal approximation to the binomial) will be calculated by treatment arm. Stratified tests comparing these rates between treatment arms will be conducted using a Cochran-Mantel-Haenszel (CMH) test.

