- **Study Period:** begins at the first study treatment dose and ends at study completion. The study period does not include the continued access period.
 - o **Study Treatment Period:** begins at the first study treatment dose and ends when the patient and the investigator agree that the patient will no longer continue study treatment. This date is to be reported on the electronic case report form (eCRF) as the Date of Discontinuation from study treatment.
- **Postdiscontinuation Follow-Up:** begins the day after the patient and the investigator agree that the patient will no longer continue study treatment.
 - Short-term follow-up begins the day after the patient and the investigator agree that the patient will no longer continue study treatment and lasts approximately 30 days.
 - o *Long-term follow-up* begins the day after short-term follow-up is completed and continues until the patient's death or overall study completion.
- Continued Access Period: begins after study completion and ends at the end of trial. During the continued access period, patients on study treatment who continue to experience clinical benefit may continue to receive study treatment (except placebo) until one of the criteria for discontinuation is met.
 - The continued access period includes continued access period short-term followup.
 - O Continued access short-term follow-up: begins the day after the patient and the investigator agree that the patient will no longer continue treatment in the continued access period and lasts approximately 30 days.

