10.1.2. Efficacy Assessments during Postdiscontinuation Follow-Up

Postdiscontinuation follow-up during the study period will be conducted as described in the Study Schedule (Attachment 1).

For those patients who discontinue study treatment without objectively measured PD, the investigative sites will continue to monitor patients and periodically evaluate tumor response approximately every 8 weeks for the first 18 months following randomization and thereafter approximately every 12 weeks by the same method used at baseline and throughout the study until the patient has objective disease progression, or until the primary analysis of PFS. In addition, anticancer therapies initiated after study treatment discontinuation will be collected during this follow-up period. After the patient has objective disease progression, radiologic imaging and photographic images are no longer required and the patient will be followed up approximately every 12 weeks until the patient's death or overall study completion.

Lilly will continue to collect survival data on all patients but may reduce data collection for other efficacy data. Lilly will notify investigators when this reduced data collection can begin.

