10.1.4. Secondary Efficacy Measures

The following secondary efficacy measures (Table JPBM.10.1) will be collected at the times shown in the Study Schedule (Attachment 1).

Table JPBM.10.1. Secondary Efficacy Endpoints

Endpoint	Definition
Overall Survival (OS)	The time from the date of study randomization to the date of death from any cause
Objective Response Rate	The proportion of patients with CR or PR according to RECIST v1.1
Disease-Control Rate (DCR)	The proportion of patients with CR, PR, or SD according to RECIST v1.1
Clinical Benefit Rate (CBR)	The proportion of patients with CR, PR, or SD ≥6 months according to RECIST v1.1
Duration of Response (DoR)	The time from the date of first evidence of a confirmed CR or PR to the date of objective progression (according to RECIST v1.1) or death from any cause, whichever is earlier

Abbreviations: CR = complete response; PR = partial response; PS = performance status; RECIST = Response Evaluation Criteria in Solid Tumors; SD = stable disease.

Overall Survival (OS): OS duration is measured from the date of randomization of any study drug to the date of death from any cause. For each patient who is not known to have died as of the data-inclusion cutoff date for a particular analysis, OS will be censored for that analysis at the last known alive date.

Objective Response Rate (ORR): The objective response rate is the percentage of patients with a best response of CR or PR.

Duration of Response (DoR): The DoR time is defined only for responders (patients with a confirmed CR or PR). It is measured from the date of first evidence of CR or PR to the date of objective progression or the date of death due to any cause, whichever is earlier. For clarity, the start date should be determined by the initial assessment of CR or PR, not the date of confirmation of CR or PR. If a responder is not known to have died or have objective progression as of the data inclusion cutoff date scores, DoR will be censored at the last complete objective progression-free disease assessment date.

Disease Control Rate (DCR): The DCR is the percentage of patients with a best response of CR, PR, or SD.

Clinical Benefit Rate (CBR): The CBR is the percentage of patients with a best response of CR or PR, or SD for at least 6 months.

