	Tumor measurement (palpable or visible)	Section 10.1.1	X	х	ONLY For patients who discontinue study treatment without objectively measured progressive disease (PD), continue to conduct tumor assessments approximately every 8 weeks for the first 18 months following randomization and thereafter approximately every 12 weeks until the patient has objective disease progression or until study completion. After the patient has objective disease progression, photographic images are no longer required and the patient will continue with post-discontinuation follow-up approximately every 12 weeks until the patient's death or overall study completion.
Tumor Assessment	Bone Scintigraphy	Section 10.1.1 Attachment 5	x	X	ONLY For patients who discontinue study treatment without objectively measured progressive disease (PD), continue to evaluate repeat bone scans approximately every 6 months until objective disease progression or study completion.
	Radiologic imaging according to RECIST	Section 10.1.1 Attachment 5	X	X	The same method of imaging used at baseline should be used for each subsequent assessment. ONLY For patients who discontinue study treatment without objectively measured progressive disease (PD), continue to conduct tumor assessment approximately every 8 weeks for the first 18 months following randomization and thereafter approximately every 12 weeks by the same method used at baseline and throughout the study until the patient has objective disease progression or until study completion. After the patient has objective disease progression, radiologic tests are no longer required and the patient will continue with post-discontinuation follow-up approximately every 12 weeks until the patient's death or overall study completion

Protocol I3Y-N	MC-JPBM	Study Period	Post-Discontinuation Short Term Follow-Up	Postdiscontinuation Long Term Follow-Up	
Post Treatment Discontinuation Study Schedule		Visit	801	802-X	
		Approximate Visit Duration (days)	30±5	Variable	
		Relative day	30		
Procedure Category	Procedure	Protocol Reference			Comments

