Progressive Disease (PD): At least a 20% increase in the sum of the diameters of target lesions, taking as reference the smallest sum on study (including the baseline sum if that is the smallest). In addition to the relative increase of 20%, the sum must also demonstrate an absolute increase of at least 5 mm. The appearance of 1 or more new lesions is also considered progression.

For equivocal findings of progression (for example, very small and uncertain new lesions; cystic changes or necrosis in existing lesions), treatment may continue until the next scheduled assessment. If at the next scheduled assessment, progression is confirmed, the date of progression should be the earlier date when progression was suspected.

Stable Disease (SD): Neither sufficient shrinkage to qualify for PR nor sufficient increase to qualify for PD, taking as reference the smallest sum diameters while on study.

Not Evaluable: When an incomplete radiologic assessment of target lesions is performed or there is a change in the method of measurement from baseline that impacts the ability to make a reliable evaluation of response.

Evaluation of Nontarget Lesions

Complete Response: Disappearance of all nontarget lesions and normalization of tumor marker level. All lymph nodes must be non-pathological or normal in size (<10mm short axis).

Non-CR/ non-PD: Persistence of 1 or more nontarget lesions and/or maintenance of tumor marker level above the normal limits.

Progressive Disease: Unequivocal progression of existing nontarget lesions. The appearance of 1 or more new lesions is also considered progression.

Not Evaluable: When a change in method of measurement from baseline occurs and impacts the ability to make a reliable evaluation of response.

Evaluation of Best Overall Response

The best overall response is the best response recorded from the start of the study treatment until the earliest of objective progression or start of new anticancer therapy, taking into account any requirement for confirmation. The patient's best overall response assignment will depend on the findings of both target and nontarget disease and will also take into consideration the appearance of new lesions. The Best Overall Response will be calculated via an algorithm using the assessment responses provided by the investigator over the course of the trial.

Time Point Response

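### The SAP closes best overall response about 30 days after treatment stops, while protocol Attachment 5 keeps it open until progression or new therapy; a first response seen later is dropped

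*SAP*

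**What the plan says.** **SAP 6.7.4.1** builds ORR, DCR and CBR from BOR. It admits "All time point responses observed while on study treatment and during the short term follow up period", provided they precede any post-discontinuation therapy. There is one exception, for patients who have surgery or radiotherapy for locally advanced disease. Confirmation of CR or PR is not required.

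**Protocol Attachment 5** defines BOR as the "best response recorded from the start of the study treatment until the earliest of objective progression or start of new anticancer therapy". It sets no limit tied to the end of treatment or of short-term follow-up.

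**Protocol 8.1** starts short-term follow-up the day after patient and investigator "agree that the patient will no longer continue study treatment and lasts approximately 30 days".

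**Protocol 10.1.2** tells sites to "periodically evaluate tumor response approximately every 8 weeks for the first 18 months following randomization", and about every 12 weeks after that, in patients who stop without objective progression. The post-discontinuation table in Attachment 1 says the same for radiologic imaging ("continue to conduct tumor assessment approximately every 8 weeks for the first 18 months following randomization") and marks it both at Visit 801 (30 ± 5 days) and at Visits 802-X.

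**Protocol 10.1.4** makes BOR the basis of the endpoint: "The objective response rate is the percentage of patients with a best response of CR or PR".

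**The concern.** Both documents open the window with study treatment and close it at new therapy. The SAP adds a further stop, the end of short-term follow-up, which applies even when the patient has neither progressed nor started another therapy. The scans this excludes are required by the protocol and will be in the database.

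The SAP does not apply the same stop elsewhere. Its PFS censoring rules (Table JPBM.6.1) and its duration-of-response rules (6.7.4.2) have no 30-day cut. A scan in long-term follow-up can therefore prolong a response or keep a patient progression-free, but it cannot establish a response.

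ORR, DCR and CBR are stated secondary objectives. With two definitions in force, the classification of the affected patients depends on which document the programmer follows. Those patients stopped all study treatment without progression, so unequal stopping between arms could move the comparison.

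**Working it through.** The plan states no expected ORR, DCR or CBR, so there is no figure to reproduce. The check compares the two windows, then the timing, then the weight of one patient.

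**1. What changes between the windows.** Take a patient who stops all study treatment without progression and starts no new therapy.

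| Scans inside the SAP window | First seen after it | ORR | DCR | CBR |
|---|---|---|---|---|
| CR or PR | anything | same | same | same |
| SD | CR or PR | lost | same | lost only if PFS is under 6 months |
| none qualifying | CR or PR | lost | lost | lost |
| none qualifying | SD | not affected | lost | lost only if PFS is 6 months or more |

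"Lost" means counted under Attachment 5 but not under the SAP. The CBR entries follow from SAP 6.7.4.1: SD of at least 6 months needs a BOR of SD together with a PFS time of at least 6 months, and that PFS time is not cut at 30 days.

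**2. When SD can be lost.** Inputs:
- Visit 801 is 30 ± 5 days after stopping (Attachment 1).
- SD needs at least 6 weeks, 42 days, from randomization (Attachment 5).
- The first on-treatment scan falls on Days 21 to 28 of Cycle 2 (Protocol 10.1.1), that is study days 28 + 21 = 49 to 28 + 28 = 56.
- Assumption: randomization and first dose fall on the same day.

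For a stop on day *s*, the Visit 801 scan falls at *s* + 30, with range *s* + 25 to *s* + 35. It reaches 42 days when:
- nominal timing: *s* + 30 ≥ 42, so *s* ≥ 12;
- latest permitted visit: *s* + 35 ≥ 42, so *s* ≥ 7;
- earliest permitted visit: *s* + 25 ≥ 42, so *s* ≥ 17.

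SD is therefore at risk for stops before about Day 12 (Day 7 to 17 allowing for the visit window), or where no Visit 801 scan is done. For example, a stop on Day 14 puts Visit 801 at about Day 44. That is before the first on-treatment scan would have been due, but past the SD minimum. A CR or PR first seen at a later follow-up scan is lost whatever the stop day.

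**3. Weight of one patient.** Protocol 12.1 plans 300 and 150 patients.
- Experimental arm: 100/300 = 0.33 points per lost response.
- Placebo arm: 100/150 = 0.67 points per lost response.

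**4. Illustrative range for ORR. Both inputs are assumptions.** Loss within an arm = (share stopping all study treatment without progression and without new therapy past the window) × (share of those whose first CR or PR comes after it).
- Low end: 2% × 0% = 0 points.
- Middle: 5% × 10% = 0.5 points, which is 1.5 of 300 or 0.75 of 150 patients.
- High end: 15% × 20% = 3.0 points, which is 9 of 300 or 4.5 of 150 patients.

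Equal shares in both arms leave the ORR difference unchanged. Only a difference between the arms moves it.

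**The case against.** **Few patients are touched.** This stands. A patient must stop without progression, take no new therapy and first reach a better category after about 30 days. Patients who stop only the blinded drug may continue the NSAI (Protocol 9.4.1.1.1.1), and Protocol 9.1 defines study treatment as blinded drug and/or NSAI, so they may remain inside the window. SAP 6.1.2 defines study treatment as the combination, which leaves this unclear.

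**A reader might infer that anyone who stops before the first on-treatment scan becomes not evaluable and fails all three rates.** The documents do not support this. Imaging is marked at Visit 801, inside the SAP window, and from about Day 12 onward that scan nominally satisfies the SD minimum. SD does not count toward ORR under either text. One reservation remains: the Attachment 1 comment gives an interval of about 8 weeks, so a site following the comment rather than the visit mark might not scan at Visit 801.

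**A reader might infer a measurable bias against the experimental arm.** More stopping for toxicity on that arm is plausible, but the documents give no rate. The introduction reports more Grade 3 diarrhea with the NSAI combination than with LY2835219 alone (25.7% against 13.6%), but at 200 mg rather than this trial's 150 mg and without an NSAI-only comparison. The background before the synopsis reports no discontinuations due to adverse events in the single-agent study.

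**A reader might infer an undisclosed departure from the protocol in force.** That cannot be shown. The protocol supplied was approved in September 2014 and the SAP is Version 5 of April 2017; amendments (a) and (b) are not supplied. SAP section 8 makes statements for Versions 1 to 3 only. Protocol 12.2.1 allows minor modifications in the SAP before unblinding, provided they are described and justified; the SAP gives no reason for this one.

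**Limiting response to scans on or soon after treatment is a defensible choice.** It is, but the SAP does not state it as a choice and does not apply it to duration of response.

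**Conclusion.** Wrong as written, with low impact. The BOR window in SAP 6.7.4.1 conflicts with the endpoint definition in protocol Attachment 5. The certain effect is on classification: a CR or PR first seen after about 30 days, before progression or new therapy, drops out of ORR, and out of DCR and CBR where no earlier SD was recorded. Loss of SD alone is confined mainly to stops before about Day 12 or a missing Visit 801 scan.

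The size for this trial cannot be derived from the documents. What is firm is 0.33 or 0.67 points per lost response; the 0 to 3.0 point ORR range depends wholly on the assumed shares. Bias between arms is possible, not established. ORR, DCR and CBR lie outside the alpha-controlled tests, so PFS and OS inference is untouched. The conclusion assumes that neither unsupplied amendment changed the Attachment 5 window.

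**What to change.** In SAP 6.7.4.1, derive BOR from every time point response between the start of study treatment and whichever comes first of objective progression and new anticancer therapy, and say explicitly that long-term follow-up scans are included. Keep the surgery and radiotherapy exception. The end of the window would then no longer depend on which drug was stopped or on how study treatment is defined.

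If the sponsor prefers the shorter window, list it with a reason in SAP section 8, state whether stopping the blinded drug alone starts the 30 days, and report ORR, DCR and CBR under the Attachment 5 window as a sensitivity analysis.

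The cost is one sentence and one derivation, with no new data. The downside is small: some responses seen after treatment has stopped will be credited to the assigned arm.

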LY2835219 is an oral, selective, and potent small molecule cyclin-dependent kinase (CDK) 4 and 6 (CDK4/6) dual inhibitor with antitumor activity within multiple preclinical pharmacology models and an acceptable toxicity profile in nonclinical species. LY2835219 mesylate has been shown to significantly inhibit tumor growth in multiple murine xenograft models for human cancer. Studies with LY2835219 across breast cancer cell lines indicate differential sensitivity to CDK4/6 inhibition based on histological and genetic characteristics. Growth inhibition in vitro across a diverse panel of 46 breast cancer cell lines, representing the known molecular subgroups of breast cancer, indicates that sensitivity to CDK4/6 inhibition is greater in estrogen receptor-positive (ER+) breast cancers with luminal histology.

LY2835219 has demonstrated evidence of single-agent clinical activity in a tumor-specific cohort of women with metastatic breast cancer (mBC). In Study I3Y-MC-JPBA (JPBA), 47 patients with a median of 7 prior systemic regimens received therapy with LY2835219. Among the 36 patients with hormone receptor-positive (HR+) mBC, there were 9 patients with confirmed partial responses (PR) for an objective response rate (ORR) of 25%. Further, of these 36 patients with HR+ mBC, the clinical benefit rate (CBR: PR + stable disease [SD] ≥24 weeks) was 61%, and the disease control rate (DCR: PR + SD) was 80.6%. A total of 14 patients were continuing treatment at the time of analysis (Patnaik et al. 2014). In the same study, LY2835219 demonstrated an acceptable safety profile for women with HR+ mBC. The most common treatment-emergent adverse events (TEAEs) were diarrhea, nausea, fatigue, neutropenia, and vomiting. There were no treatment discontinuations attributable to an AE. The clinical activity and safety profile support further evaluation of LY2835219 in mBC.

Non-steroidal aromatase inhibitors (NSAI, letrozole and anastrazole) are approved and commonly used endocrine therapy in the first-line setting for postmenopausal women with HR+ mBC. The evaluation of LY2835219 in combination with an NSAI is of interest since both classes of drugs have acceptable and distinct safety profiles. The current study will assess if additional clinical benefit may be achieved in this disease setting with this drug combination.

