12.1. Determination of Sample Size

The primary objective of this study is to compare LY2835219 plus NSAI versus placebo plus NSAI in terms of PFS in postmenopausal women with HR+, HER2- locoregionally recurrent or metastatic breast cancer who have not received prior endocrine therapy in this disease setting.

The study will enroll approximately 450 patients in 2:1 randomization (300 patients in LY2835219 plus NSAI and 150 patients in placebo plus NSAI). Patients will be randomized using the following stratification factors: nature of disease (visceral metastases versus bone-only metastases versus other) and prior (neo)adjuvant endocrine therapy (aromatase inhibitor therapy versus other versus no prior endocrine therapy).

A group-sequential design of the primary endpoint will be used to accommodate an event-driven plan for the interim and primary PFS analyses (see Section 12.2.6 for details). The primary PFS analysis will be performed after approximately 312 PFS events have occurred (that is, a 30% censoring rate). Assuming a hazard ratio of 0.714, this sample size yields at least 80% statistical power to detect superiority of the LY2835219 plus NSAI arm over the placebo plus NSAI arm with the use of a 1-sided log-rank test and a cumulative type I error of 0.025. If the true median PFS for the placebo plus NSAI arm is 10 months, then the hazard ratio of 0.714 amounts to an approximately 4-month (40%) improvement in median PFS for the LY2835219 plus NSAI arm under an additional assumption of exponential survival distribution. Assuming approximately 10% screening failure, the study will enter approximately 500 patients.

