6.7. Efficacy Analyses

6.7.1. General Considerations

6.7.1.1. Population

Unless otherwise noted, all efficacy analyses will be performed on the ITT population.

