6.7.1.3. Hypothesis Tests and Confidence Intervals for Efficacy Data

Unless otherwise noted, all hypothesis tests will be performed at the one-sided .025 level and all confidence intervals (CIs) will utilize a 95% confidence level.

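### The normal-approximation interval for the disease control rate is slightly mis-centred at the rates the plan implies; Wilson score intervals would correct this at no cost (minor).

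*SAP*

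**What the plan says.** SAP Section 6.7.4.1 covers objective response rate (ORR), disease control rate (DCR) and clinical benefit rate (CBR). Its rule for the intervals is: "For each of these rates, point estimates and confidence intervals (using the normal approximation to the binomial) will be calculated by treatment arm". Section 6.7.1.3 adds that "all confidence intervals (CIs) will utilize a 95% confidence level" unless otherwise noted. The text does not name Wald, but that is what the phrase normally means.

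On denominators, SAP Section 6.7.1.1 says: "Unless otherwise noted, all efficacy analyses will be performed on the ITT population". Protocol Section 12.1 plans arms of about 300 and 150. DCR is defined by best overall response (BOR): "Disease control rate is the proportion of patients with a BOR of CR, PR, or SD". Not evaluable is a separate BOR category, so such patients stay in the denominator as failures. ORR has a second denominator: "thus ORR will be reported for both the ITT population and the subset of patients with measurable disease". The size of that subset is not stated.

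The between-arm comparison is separate: "Stratified tests comparing these rates between treatment arms will be conducted using a Cochran-Mantel-Haenszel (CMH) test". Protocol Section 12.2.7.2 had planned a normal approximation for the difference in rates; I take the later SAP as governing. All three rates fall under Other Secondary Endpoints, outside the alpha-controlled testing of PFS and overall survival.

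Neither document gives an expected DCR for this trial or any coverage or width for these intervals. The only DCR on record comes from 36 HR+ patients in the earlier single-agent study, where "the disease control rate (DCR: PR + SD) was 80.6" per cent.

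**The concern.** The Wald interval is centred on the observed proportion and takes its width from the estimated variance. As the true rate nears 100%, the sampling distribution becomes skewed and the interval misses more often than stated, mostly because its lower limit is too high. DCR is the rate at risk here. It counts every patient whose best response is stable disease or better, and this is a first-line population in which both arms receive an active endocrine therapy.

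What is at stake is how accurately a named secondary endpoint is described. A lower limit that is too high overstates the least favourable disease control rate compatible with the data. No test, error rate or sample size depends on it.

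**Working it through.** **1. Inputs.**
- SAP Section 5.2: exponential PFS, placebo median 10 months, hazard ratio 0.67.
- Protocol Section 10.1.1: first scan between Day 21 and Day 28 of Cycle 2, which with 28-day cycles is day 49 to 56.
- SAP Section 6.1.2: one month is 365/12 = 30.42 days.
- Protocol Section 12.1: arms of 150 and 300.

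There is no stated figure for these intervals to reproduce. The PFS inputs do reproduce: 10/0.67 = 14.9 months, which matches the SAP's improvement of about 5 months.

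**2. What DCR do these inputs imply?** A patient who has progressed or died by the first scan cannot have a best response of stable disease or better. The progression-free proportion at that scan is therefore a rough upper bound:

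S(t) = exp(−ln 2 × t / median)

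- Placebo: t = 49/30.42 = 1.61 months gives 89.4%; t = 56/30.42 = 1.84 months gives 88.0%.
- Abemaciclib, median 14.9 months: 92.8% and 91.8%.

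Patients who are not evaluable lower these further.

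**3. Intervals compared** (z = 1.96, p̂ = x/n).
- Wald: p̂ ± z√[p̂(1−p̂)/n]
- Wilson: {p̂ + z²/2n ± z√[p̂(1−p̂)/n + z²/4n²]} / (1 + z²/n)

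At 135/150:
- Wald: 0.900 ± 1.96 × √(0.09/150) = 0.900 ± 0.048, or 85.2-94.8%.
- Wilson: centre (0.900 + 0.0128)/1.0256 = 0.890, half-width 0.0484, or 84.2-93.8%.

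| Observed | Wald width (points) | Wilson width (points) |
|---|---|---|
| 121/150 | 12.64 | 12.57 |
| 132/150 | 10.40 | 10.44 |
| 135/150 | 9.60 | 9.69 |
| 276/300 | 6.14 | 6.19 |

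The widths almost coincide. What differs is the location, by about 1 point at 135/150 and about 0.5 point at 276/300 (Wald 88.9-95.1%, Wilson 88.4-94.6%).

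**4. Exact coverage.** For true rate p, coverage is the sum of Binomial(x; n, p) over all x whose interval contains p. Single values oscillate with p, so I average over a range.

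| n | True DCR | Wald | Wilson |
|---|---|---|---|
| 150 | 78-83% | 94.3% | 95.1% |
| 150 | 84-89% | 94.0% | 95.1% |
| 150 | 85-90% | 93.9% | 95.1% |
| 150 | 90-95% | 93.1% | 95.2% |
| 150 | 95-98% | 90.2% | 95.4% |
| 300 | 78-83% | 94.7% | 95.0% |
| 300 | 88-93% | 94.2% | 95.1% |
| 300 | 90-95% | 94.0% | 95.1% |
| 300 | 95-98% | 92.8% | 95.2% |

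**5. Direction of the misses.** For n = 150 over 85-90%, the Wald lower limit lies above the true rate 4.7% of the time and the upper limit lies below it 1.4% of the time; each should be 2.5%. Wilson leans mildly the other way, at 1.9% and 3.0%.

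**6. Limits above 100%.** With p̂ < 1, the Wald upper limit passes 1 when p̂ > n/(n + z²). That is 97.5% for n = 150, first reached at 147/150 (interval 95.8-100.2%), and 98.7% for n = 300, first reached at 297/300. The chance of at least 147/150 is about 0.001-0.005% at a true DCR of 88-89%. The chance of at least 297/300 at 93% is below 0.0001%.

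**7. Mid-range rates.** At the earlier study's CBR of 61%, Wald coverage is 94.5% (n = 150) and 94.9% (n = 300). At its ORR of 25% it is 93.7% and 94.5%; Wilson at 25% and n = 150 gives 94.1%, so little is gained there.

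**The case against.** The strongest reply is that this is a preference between two standard methods. The SAP names a conventional interval in advance, the arms are compared by a test that does not use it, and only PFS and overall survival are alpha-controlled. Limits move by a point or less. At single rates Wald can even do better: at n = 150 and a true rate of 88%, it covers 94.4% and Wilson 94.2%. All of this is correct, and it keeps the point minor. It does not remove the point, because the average shortfall and the one-sided lean are systematic over the range the plan implies, and correcting them costs nothing.

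A reader might also infer that the planned intervals are too narrow, or that they will show impossible values. The documents do not support either. In the range implied by SAP Section 5.2 the widths are almost equal and limits above 100% are practically excluded. Wald coverage does fall to about 80% at n = 150, but only at a true DCR of 98%. Under the exponential model, even 95% progression-free at the first scan needs a median PFS of ln 2 × 1.61/0.0513 = 22 months to ln 2 × 1.84/0.0513 = 25 months, against planned medians of 10 and about 15.

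Nor can the 80.6% from the earlier study simply be projected upwards. Those patients all received LY2835219, so the figure says little about the placebo arm, where the smaller sample matters most. The SAP's PFS assumptions are the firmer basis, and I use them here.

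**Conclusion.** The point holds as a minor one and chiefly concerns DCR. At the rates implied by the SAP's own assumptions, the planned 95% interval covers about 94% on average, and its misses fall mainly on the side that flatters disease control. ORR and CBR in mid-range are hardly affected. The intervals are descriptive and no trial conclusion depends on them.

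This rests on four assumptions: that Wald is the approximation meant; that the arms are close to 150 and 300; that PFS is exponential with the planned median and hazard ratio; and that the progression-free proportion at the first scan bounds DCR. If either arm did clearly better than planned and its DCR passed 95%, the shortfall would grow, to an average of 2.2 points at n = 300 and 4.8 points at n = 150 over 95-98% (95.0 − 92.8 and 95.0 − 90.2).

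**What to change.** In SAP Section 6.7.4.1, replace the normal approximation with Wilson score 95% intervals for the per-arm rates. DCR is the reason for the change. Using one method for all three rates is simpler and also covers ORR in the measurable-disease subset, whose size is not given. Keep the stratified Cochran-Mantel-Haenszel test.

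The cost is one phrase and one software option. Point estimates, sample size, alpha control and the between-arm comparison do not change.
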